FIOC was designed specifically to aid development of positive coparenting alliances between at-risk (unmarried, uncoupled, low income) African American mothers and fathers having a first baby together. In the RCT, randomly-assigned control group families (referred by already-known referral agents and partners who worked closely with our team on the pilot projects) will receive Pinellas County services as-usual for pregnant parents and assistance of a Resource and Referral Navigator for referrals to desired community services ("Treatment as Usual", or TAU). The remaining (experimental group) families will receive the same services and aid, plus the 6-session FIOC prenatal intervention with a post-natal booster session. The first 150 families consented in will be assigned to groups via urn randomization. The remaining families recruited up to 170 will be assigned to the experimental (FIOC) group to achieve balance in the number of families contributing postnatal follow-up data longitudinally in the two groups to allow minimally sufficient statistical power for analyses. The FIOC intervention addresses the importance of safe, healthy families for early infant development, the impact a cooperative and sustained coparenting alliance can have in promoting positive infant development, challenges unmarried parents face cultivating a coparenting alliance together when their commitment to one another as romantic or married partners is in doubt, and ways to surmount these obstacles, maintain rapport, and sustain a strong alliance.

All 170 participating families, both at intake (prior to the intervention) and then again at 3 and 12 months post-partum, will report beliefs about fatherhood; extent of depressive symptomatology; and quality of the mother-father partnership. State-of-the-field coparenting observations will be conducted at each follow-up, along with measures of parental stress, intimate partner violence (IPV), perceived coparenting support, father engagement, and infant socioemotional adjustment. Analyses will examine impact of the intervention on promoting more supportive, coordinated post-partum coparenting alliances and more positive adult and infant outcomes. Exploratory analyses will examine links between father involvement and child adjustment and whether this coparenting intervention also stands to prevent IPV.

2. Background information

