- Aim 1: To determine the efficacy of FIOC in positively affecting first-year coparenting of unmarried African American parents, relative to early coparenting of comparison families
Hypothesis 1: Families who participate in FIOC will demonstrate more cooperation and better communication in their post-natal coparenting systems at 3 and 12 months post-partum than families receiving TAU
- Aim 2: To determine the efficacy of FIOC in affecting first-year parental adjustment.
Hypothesis 2: Mothers and father who participate in FIOC will show greater decreases in depressive symptomology from prenatal to postnatal assessments than parents receiving TAU.
Hypothesis 3: Mothers and father who participate in FIOC will show lower levels of parenting stress at 3 and 12 months than families receiving TAU.
- Aim 3: To determine the efficacy of FIOC in affecting early child outcomes.
Hypothesis 4: Infants whose coparents participate in FIOC will show a more advanced

triangular capacity at 3 and 12 months

Hypothesis 5: Infants whose coparents participate in FIOC will show better regulatory and socioemotional competence at 12 months than control group children.

- Aim 4: To determine the efficacy of FIOC in affecting father involvement
Hypothesis 6: Fathers who participate in FIOC will show greater involvement at 3 and 12 months post-partum
- Aim 5: To determine whether increased father involvement is associated with better socioemotional adjustment by the baby
Hypothesis 7: Children of more involved fathers will show greater regulatory and socioemotional competence at 12 months post-partum
- Aim 6: To explore whether the FIOC intervention has an impact on the emergence of intimate partner violence (IPV)
Hypothesis 8: IPV will be more likely to emerge during the child's first year among TAU families than among families who complete the FIOC intervention
- Aim 7: To determine whether enrollment numbers, randomization rates, retention rates, and comparative RCT outcomes differ as a function of active versus passive recruitment methods for unmarried mother-father dyads.
Hypothesis 9: Proportions of enrollment and randomization and retention rates will favor families identified via self-referral (passive recruitment), while outcomes for families completing the intervention will not differentiate the two groups.

4. Study design including information needed to answer the research questions:

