This is a prospective longitudinal study using a pre-post randomized controlled treatment design that will allow comparisons of the extent to which study participants in experimental and control groups show pre-to-post changes in family functioning.

All families are seen initially for a PRE Intake assessment (Time 1), during which mothers are screened for prior or active IPV using valid, standardized instruments, an IPV Screen and the Revised-Conflict Tactics Scale (CTS2). If mothers report a history of IPV, they may under specified circumstances still be eligible to participate depending upon results of an assessment performed by trained project staff using the Danger Assessment Scale (DAS; Campbell 2003) as a screening instrument (see inclusion and exclusion criteria). If certain indicators are present in the mother's IPV screen/CTS2 assessments at baseline, the father will not be given the IPV screen/CTS2. If the father is not be given the IPV screen/CTS2 at pre-assessment, he will not be given the IPV screen/CTS2 at either post assessment time-point. The decision about whether to enroll a family reporting IPV is made in consultation with Co-PI [name] after the session concludes. Families are notified that they will receive a phone call within 48 hours appraising them of whether or not they have been chosen to take part in the study and, if they are chosen, which group (treatment or control) they will be assigned to. All families for whom levels of IPV are NOT of substantive concern and who are not found ineligible for other valid exclusion factors are randomized to one of the 2 groups and notified of their assignment. Those for whom IPV is a concern or who are ineligible for other reasons are notified that they were not selected.

For those to be enrolled (projected to be the overwhelming majority of all screened families who complete the intake process), subjects are assigned to treatment conditions through urn

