Child Outcome Measures at Time 3: An adapted version of the Infant Toddler Social Emotional Assessment (ITSEA; Carter & Briggs-Gowan, 2006), comprised of the full Brief Infant Toddler Social Emotional Assessment (BITSEA) and select additional scale items from the longer ITSEA instrument, was developed in consultation with the scale’s author. The instrument measures both social-emotional/ behavioral problems and delays in competency for children ages 12-36 months. It is a 71-item parent-report index constituting of six sub-scales: Problem behavior, competence, compliance, negative emotionality, aggression, and sleep.

5. Sample size justification:

We employed a computer program provided by Murphy et al. (2009; the same information is available from the tables in Cohen, 1988) to compute the significance level required for a projected sample size, incorporating attrition estimates, of $N=120$ (60 each in the treatment and control groups, respectively). Assuming the null effect hypothesis and alpha set at .05 and power of .8, an $F(1, 117)$ of 7.74 with a $d = .514$ is required for significance. Keeping the null hypothesis test, alpha .05 and lowering power to .5, an $F(1, 117) = 4.03$ with a $d = .37$ is required for significance. Drawing on effect size estimates from the feasibility study, even with low power (.5) resulting in a $d=.37$ we would be positioned to establish the effect of the FIOC treatment for 10 of the 12 FIOC variables (10 of the 12 SCID-evaluated couple problem-solving and communication variables summarized earlier had a d greater than .33).

6. Sample type or inclusion and exclusion criteria for participating in the research:

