Exclusion Criteria: Families will be excluded if they: 1) demonstrate evidence of psychotic symptoms or suicidal ideation on the Brief Symptom Inventory; 2) either partner has recently (over the past 12 months) been arrested and convicted for violence (assault) perpetrated against someone other than a current or former partner who is the co-parent of one of their children; or 3) are deemed high risk or in need of more intensive intervention. Risk determination is made by weighing the parent's report on the Danger Assessment Scale (DAS). As a rule of thumb, a DAS score of 9 or higher will result in automatic exclusion from the study. However, it is also possible that even with a score below 9, the parent may disclose one or more of the following issues during administration of the DAS, any of which would result in exclusion from the study: 1) parent reports she has required medical care because of significant injuries due to his violence, 2) parent says she fears for her life, 3) parent reports that the partner has threatened with a weapon and owns a gun or has a gun in the household; 4) parent reports that the partner has threatened to kill her; 5) parent reports that violence has escalated recently; 6) parent reports the partner's use of illicit drugs such as cocaine, methamphetamines, hallucinogens, or opiates .

7. Expected results of the research (reports, materials, discussion papers, contributions to theory):

Results will equip the research team with answers to study objectives and determine whether there would be value in studying the curriculum in a future multi-site implementation trial.

8. Study Staff

- 1. [name].**, P.I. Will provide all project oversight; serve as IRB officer; ensure research integrity and compliance; chair senior staff and other relevant team meetings; supervise fidelity-monitoring efforts; oversee proper implementation of all protocols, data collection, evaluation of videotaped infant and family data, data management and entry, analyses, report writing, and dissemination of findings.

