## **Cover Letter**

### **Statistical Analysis Plan**

**Document Date 1.31.2022**

**NCT03097991**

### **FIOC Statistical Analysis Plan**

- Initial descriptive summations and simple statistical tests will compare groups.

- Primary Aims 1-4: Effects of the intervention. To examine if coparenting and individual adjustment outcomes are superior for FIOC families than for control group families at 3- and 12-months post-partum two-sided independent sample t-test for equivalence will first be employed for single time point comparisons. We will test hypotheses further using linear or generalized linear models to control for potential confounding and account for imbalance between the two treatment conditions.
- For longitudinal outcomes that are continuous (measured at Baseline; 3; and 12 months post-partum) we will use repeated measures analysis of covariance (ANCOVA; Crowder & Hand, 1990) to detect if treatment and control groups perform differently at any time points. For longitudinal outcomes that are categorical, generalized linear model (GLM, McCullagh & Nelder, 1989) will be used for the same purpose. Repeated measures ANCOVA and GLM allow us to account for correlation between repeated measures and detect possible moderating/confounding between treatment effects and subject individual differences. Multiple comparison adjustment will be addressed in analyses. We will report significance under both regular (.05) and Bonferroni-adjusted alpha.
- Exploratory Aim 1: To examine whether extent of father engagement is associated with better infant socioemotional adjustment regression analyses will examine variance in infants' 12-month ITSEA Internalizing, Externalizing, Dysregulation and Competence scores explained by 3- and 12-month father engagement.
- Exploratory Aim 2: To examine whether FIOC prevents the emergence of IPV and help to prevent future IPV in couples where it was previously reported, we will first explore simple chi-square analysis to compare FIOC and TAU conditions on the binary variable of any instance of physical violence between partners reported on the CTS2 over the 12 months of follow-up. Next,

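### Up to 20 families are placed in FIOC without randomisation, and the SAP does not separate them from the randomised comparison

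*Protocol*

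**What the plan says.** Protocol section 1 (General Information) sets two allocation rules in sequence. First: "The first 150 families consented in will be assigned to groups via urn randomization". Then: "The remaining families recruited up to 170 will be assigned to the experimental (FIOC) group to achieve balance in the number of families" contributing follow-up data. The stated reason is to give the analyses enough power. The same section has all 170 families assessed at intake, 3 months and 12 months, without distinguishing how they were assigned.

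Protocol section 4 (Study design) does not carry the second rule. It says that all families who pass the IPV and other eligibility checks "are randomized to one of the 2 groups and notified of their assignment".

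Protocol section 5 (Sample size justification) bases power on 120 analysed families, "60 each in the treatment and control groups, respectively". It does not say whether these come from 150 or 170.

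The SAP asks for Aims 1-4 whether "coparenting and individual adjustment outcomes are superior for FIOC families than for control group families at 3- and 12-months post-partum", using two-sided t-tests first and then linear or generalized linear models with unnamed covariates. For IPV it plans a chi-square test to "compare FIOC and TAU conditions on the binary variable of any instance of physical violence between partners", followed by regressions that include baseline CTS2. It defines no analysis population and has no allocation flag, enrolment-period term or randomised-only analysis.

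**The concern.** The added families were placed in FIOC by rule, all after the first 150, and no family was assigned to TAU alongside them. Anything that changed over the enrolment period therefore falls on one arm only for this group. They also bypass the urn's balancing on children from prior unions and frequency of IPV.

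Once the rule is in force, staff can know that the next family will receive FIOC before its eligibility is settled. This is an inference from section 1; the documents do not describe it. It has some relevance because one exclusion ground, families who "are deemed high risk or in need of more intensive intervention", involves weighing evidence and a consultation with the Co-PI as well as a score threshold.

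Two other late changes could also distinguish these families: the media campaign in Appendix A, and the telehealth option in section 4. The documents do not say that the added families came by either route.

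If the added families would have done better anyway, the pooled contrast shows a false benefit. If they would have done worse, it hides a real one. If they do not differ there is no bias, but a pooled analysis cannot show that. Either way, the result would be reported as an RCT efficacy finding.

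**Working it through.** **Inputs from the documents.** 150 families urn-randomised; up to 170 in total (section 1). 60 analysed per arm, alpha .05, F(1,117) = 7.74 with d = .514 at power .8, and F(1,117) = 4.03 with d = .37 at power .5 (section 5). Two-sided t-test (SAP).

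**Assumptions.** The urn splits 75/75. The 60 analysed FIOC families include some of the added ones. The added families differ from the randomised ones by D standard deviations for reasons unrelated to FIOC. The documents give no value for D, so a range is used.

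**Step 1. The plan's own figures.** d = 2·√(F/df). 2·√(7.74/117) = 0.514 and 2·√(4.03/117) = 0.371, both as stated. The noncentral t with 117 df and 60 per arm gives power 0.797 at d = .514 and 0.520 at d = .37, close to the stated .8 and .5.

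**Step 2. Share not randomised.** 170 − 150 = 20. FIOC enrols 75 + 20 = 95, so 20/95 = 21%.

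**Step 3. Share among those analysed.** Reaching 60 and 60 from 75 TAU and 95 FIOC implies retention of 60/75 = 80% and 60/95 = 63%. Pro rata, the 60 FIOC families then hold 60 × 20/95 = 12.6 added and 47.4 randomised. The extreme is all 20 retained, leaving 40 randomised. That needs 100% retention of the added families against 40/75 = 53% of the randomised FIOC families, so it is an upper bound.

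**Step 4. Bias, type I error and power.** Bias = (added completers/60) × D. The noncentrality is the net effect × √(60·60/120) = net effect × 5.477. The net effect is the bias under the null, and .514 minus the bias when D is adverse.

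| D (SD) | Bias, pro rata | Type I error | Power at .514, adverse D | Bias, all 20 | Type I error | Power at .514, adverse D |
|---|---|---|---|---|---|---|
| 0.2 | 0.04 | 5.6% | 0.73 | 0.07 | 6.5% | 0.68 |
| 0.3 | 0.06 | 6.4% | 0.69 | 0.10 | 8.4% | 0.61 |
| 0.5 | 0.11 | 8.8% | 0.60 | 0.17 | 14.8% | 0.47 |
| 0.8 | 0.17 | 15.0% | 0.47 | 0.27 | 30.5% | 0.27 |

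Simulation of the all-20 case (100,000 t-tests per value of D) gives type I errors of 6.5%, 8.3%, 14.2% and 28.0%. The simulated values are the more accurate at large D, because mixing two groups widens the FIOC variance.

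**Step 5. Power on the randomised families alone.**

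| TAU vs FIOC analysed | Power at .514 | Power at .37 | d for 80% power |
|---|---|---|---|
| 60 vs 60 | 0.797 | 0.520 | 0.516 |
| 60 vs 47 (pro rata) | 0.744 | 0.469 | 0.551 |
| 60 vs 40 (all 20 retained) | 0.703 | 0.434 | 0.578 |

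Under equal retention everywhere (120/170 = 71%), the full set is 53 vs 67 with power 0.79 at d = .514, and the randomised set is 53 vs 53 with power 0.75.

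These figures concern continuous outcomes. The IPV chi-square has the same structural problem, but the documents give no event rate from which to size it.

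**The case against.** The size of the harm is wholly assumed. No section gives a difference between added and randomised families, and at 0.2-0.3 SD with pro rata retention the type I error is 5.6-6.4%, little above nominal. Section 5 does not tie 60 per arm to 170 families either: 120/150 is 80% retention, so the target could have been set on randomised families alone. All of this stands, and it is why the figures above are conditional. It does not remove the problem, because section 1 says the extra families are there to supply follow-up data and power for the analyses.

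A second objection is that the SAP plans models to control confounding and imbalance. Baseline depression, relationship quality, observed coparenting and CTS2 are available for this, and adjusting for them could remove part of any prognostic difference. But the covariates are unnamed, and the first-step t-tests and the chi-square are unadjusted. An entry-period effect also cannot be separated from treatment for families with no concurrent controls.

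Third, the risk-based exclusion is largely specified: section 6 gives a Danger Assessment Scale threshold and six listed disclosures. Some judgement remains, since the threshold is called a rule of thumb and section 4 has enrolment of families reporting IPV decided in consultation. The foreknowledge argument is therefore secondary, and the main point does not depend on it.

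**Conclusion.** The concern holds. Up to 20 FIOC families are not randomised, the SAP does nothing to separate them, and sections 1 and 4 of the protocol disagree on who is randomised. These three facts come directly from the text.

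The bias itself is possible, not demonstrated, and its direction is unknown. Under the stated assumptions it runs from negligible (0.04 SD at D = 0.2, pro rata) to serious (0.27 SD at D = 0.8, all 20 retained). An adverse D of only about 0.15-0.17 SD would cancel the power at d = .514 gained by adding the families, so the benefit of pooling is fragile.

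The comparison among the first 150 families remains randomised, so the trial can still deliver a valid primary result if the SAP specifies it. The point should be settled before the efficacy results are reported.

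**What to change.** In the SAP:

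- Define the urn-randomised families, analysed in the arm assigned, as the primary population for Aims 1-4 and the IPV contrast.
- Add an allocation flag, and report the analysis of up to 170 families as supportive and explicitly non-randomised.
- Report retention by arm among the 150 and restate power on that set.
- For Aim 7, leave the directly assigned families out of randomisation rates and out of any FIOC-versus-TAU contrast by recruitment route. They can stay in enrolment and retention summaries and in the part of Hypothesis 9 that expects "outcomes for families completing the intervention will not differentiate the two groups", since that compares routes among intervention completers.

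In the protocol, reconcile sections 1 and 4 on which families are randomised.

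The cost is SAP wording, one variable and a revised power statement; no new data are needed. The loss of power at d = .514 is about 0 to 9 points: none if 60 randomised families per arm are available, 0.797 − 0.703 = 0.094 in the extreme case. Retention by arm, which the documents do not give, decides where in that range it falls.

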For African American men, prenatal engagement is an important prognosticator of things to come. Early Head Start Research and Evaluation Project data indicate that in contrast to White and Hispanic fathers, whose non-residential status at birth is the best predictor of the timing of eventual inaccessibility to their children, the best predictor for African American fathers is whether they were involved during the pregnancy, not non-residential status at birth (Lamb et al, 2009). Although African-American children are far more likely than Asian, Hispanic, or White children to know non-co-resident biological fathers (Avenilla et al., 2006), the nature of the coparenting alliance unmarried parents create (or fail to create) is a critical determinant of whether fathers stay involved. Coparenting between non-co-resident FFWB parents during infancy strongly predicted later father involvement, but early father involvement only weakly predicted later coparenting (Carlson et al., 2008). Prenatal fatherhood programs that promote father involvement without also helping mothers and fathers coordinate as coparents hence may also miss their mark (McHale, 2007; 2009); unwelcome father involvement triggers more, not less, coparenting conflict (Talbot et al., 2009). In the lone fatherhood intervention study examining both father involvement and coparenting as distinct outcomes, Doherty (2005) found desired intervention effects on early father engagement -- but no effect on coparenting.

In Pro00004412 (supported by funding from the Brady Education Foundation), we established that the FIOC intervention successfully promoted improvements in unmarried African American parents' rapport, problem-solving and communication. In Pro00019385, New Applications for Promoting Coparenting Alliances in Unmarried Couples, we established the feasibility of successfully delivering the intervention with positive outcomes to parents positive for minimal (or situational) intimate partner violence (IPV). The NIH study protocol (assessment, intervention, safety plan) diverges very little from the prior studies. The main difference is more extensive pre- and post- assessments and, of course, random selection for participation in the experimental group to receive the FIOC intervention. Any referred families with more significant and serious IPV are ineligible for participation in the study, as they were in the prior projects.

3. Research questions, objectives and purpose:

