randomization, to maximize the likelihood that treatment groups will be balanced with respect to demographic variables (presence of children from prior unions) and prognostic variables (frequency of IPV). We will use a Microsoft Access-based program previously developed for the Yale Department of Psychiatry NIDA-funded Psychotherapy Development Center and used in prior studies by Co-PI [name]. In urn randomization, an algorithm modifies ongoing randomization probabilities based on prior composition of treatment groups, and maximizes multivariate equivalence of treatment groups (Stout et al., 1994). Thus, urn randomization offers the benefits of balancing allocation of important prognostic variables in treatment groups, while still retaining other benefits of random assignment (Wei, 1978).

Once enrolled, parents assigned to the treatment group are contacted by the Intake Coordinator or Resource and Referral Navigator who introduces their mentors and delivers the participants' gift cards for completing the intake assessment. Mentors arrange two initial 1-on-1 mentorship sessions with the parents, as per the FIOC protocol, after which the FIOC intervention commences. Families randomized to the control group are contacted by the Intake Coordinator or Resource and Referral Navigator, who schedules a meeting to deliver gift cards for completing the intake assessment. The R&R Navigator also provides a listing of existing Pinellas County Services and offers parents the opportunity to contact her at any time for assistance with referrals to Pinellas County services for pregnant or parenting families. All families, regardless of assignment, are also reminded about the follow-up assessments that will be completed at 3 months post-partum; and at 12 months post-partum. A formal check-in will be completed at 1-month post-partum (Congratulations on the birth card sent), and episodic newsletters and reminder texts (for families consented after January 30, 2017) will be sent at staged intervals to help keep in touch. Texts or phone calls to keep in touch will be sent to female participants by female staff only to ensure comfort of research participants.

All study participants will be offered the opportunity to be seen for initial assessments, follow-ups and mentoring sessions in person or via the Microsoft Teams platform.

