An important aspect of this work is carefully monitoring the experiences of the enrolled families. The entire project team will be involved in this endeavor, but major responsibilities for connecting with families will be shouldered by the Recruiter/Intake Coordinator. Her role involves talking with parents who have signaled their interest and enrolling them in the study. Each week's recruitment, enrollment and retention activities are reviewed by the project operations team, and appropriate strategies for improvement are identified and implemented. Retention of parents who have been randomized to the control condition is always of special concern; in this project, retention of control group parents is promoted by episodic contacts with the assigned Resource and Referral Navigator, a Congratulations card after the baby is born, and episodic staged reminder texts and newsletters. Retention of parents who have been randomized to the intervention condition is likewise supported by a R&R Navigator, and Mentors are also important to retention efforts with intervention group families. All families will be contacted by female Resource and Referral Navigator and mentors throughout the study duration as is needed for scheduling, follow-ups on missed appointments, formal check-ins at 1 and 9 months postpartum, and planning for 3- and 12-month post-partum follow-up visits. When deemed necessary to ensure retention, fathers will be contacted for the above purposes by male staff members. **In addition, families will be contacted more frequently (at least once-monthly) during periods of elevated local or national stress or unrest to ensure any emergent, unforeseen needs they may have for new resources get addressed.** Should challenging issues arise, Clinical Supervisors, kept informed of family situations by project Mentors during weekly supervision meetings, help guide Mentors in responding to clinical challenges and monitor potential adverse effects in an ongoing way during supervision meetings. Monitoring can also occur at any time and with any required frequency in the event a situation qualifying as an adverse event occurs in between weekly supervision meetings. If clinically concerning scenarios of any sort arise, the Mentors first attempt to resolve the situation through consultation with clinical supervisors, who in turn report weekly (and more often if needed) to the PI and Co-PI. If resolution of a clinically-concerning scenario cannot be reached through use of supervision and rises to the level of an adverse event, the clinical team (co-PI and clinical supervisor informed by the Mentors) and PI coalesce to form a plan that is then reported to the project's Data and Safety Monitoring Board, who comment on the plan and provide guidance. Expert consultant [name] can also be available to consult as needed on cases requiring additional expert input. Families will be retained in the project so long as they continue to express interest in participation and can continue to be safely enrolled. If a family must be withdrawn from the project based on assessments of concerns around safety, unresolved trauma, or other level of psychological or medical need beyond that which the project can safely provide, appropriate community resources and referrals are provided to the parents.

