we will conduct a linear regression model with intervention group and baseline CTS2 scores as predictors and CTS2 12-month scores as outcome variables. Next, hierarchical regression will be used to assess the main effects of the intervention group and severity of previous violence (reported on the CTS2 at baseline) on the severity of IPV over the 12 months of follow-up, and the interaction effect of FIOC x previous IPV on IPV severity at follow-up.

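### Hypothesis 8 compares TAU families with FIOC completers, and the SAP's by-condition IPV comparison neither states analysis by assigned arm nor separates the non-randomised FIOC families

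*Protocol*

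**What the plan says.** Aim 6 (Protocol section 3) asks, as an exploration, whether FIOC affects the emergence of IPV. It sets no completion condition. Hypothesis 8 beneath it does: IPV should be more likely "among TAU families than among families who complete the FIOC intervention". Hypotheses 1 to 6 speak of those who participate in FIOC, not those who complete it. Hypothesis 9 also mentions completing families, but it contrasts recruitment routes, not arms. Neither document defines completion.

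The SAP, dated later than the protocol, handles this aim as Exploratory Aim 2. It begins with a chi-square test "to compare FIOC and TAU conditions on the binary variable of any instance of physical violence between partners reported on the CTS2"; the period covered is the follow-up year. Then "we will conduct a linear regression model with intervention group and baseline CTS2 scores as predictors", followed by a hierarchical regression with baseline violence and its interaction with FIOC. No analysis set is named for any of the three.

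Protocol section 1 assigns the first 150 families by urn randomisation. Families recruited after that, up to 170, "will be assigned to the experimental (FIOC) group to achieve balance in the number of families contributing postnatal follow-up data". The SAP does not say whether these families enter the IPV comparison.

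**The concern.** Randomisation protects a comparison of families by the arm they were assigned to. Hypothesis 8 asks for something else: everyone in TAU against a subset of FIOC chosen by what happened after assignment. If violent families are less likely to finish the programme, completers will show less violence than TAU even when FIOC does nothing.

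The SAP's wording avoids that contrast without expressly replacing it, so an analyst could follow either text and claim to have followed the plan. Even the better reading, all FIOC against all TAU, mixes up to 20 families placed in FIOC without randomisation with those allocated by urn. They were recruited later and have no concurrent TAU counterparts.

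The aim is exploratory, but whether a coparenting programme affects partner violence bears on safety. The reader of the result should know which comparison produced it.

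**Working it through.** **The plan's own figure.** Protocol section 5 projects 120 families ("60 each in the treatment and control groups, respectively") and d = .514 at 80% power. This reproduces: 2 × √(7.74/117) = 0.514, and a two-sided t-test with 60 per arm and 117 degrees of freedom has power 0.797. It is a general statement and says nothing about IPV; only the 60 per arm is used below.

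**Inputs.** From the documents: 150 randomised families, up to 20 placed directly in FIOC, 60 followed per arm. Assumed: 75 randomised per arm; IPV proportion p = 20% in both arms (no true effect); FIOC non-completion L; and s, the ratio of non-completion in violent to non-violent families.

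**Step 1. Completers against all TAU (the Hypothesis 8 contrast).** Let u be non-completion among non-violent families and w = s × u among violent ones. Then L = p × w + (1 − p) × u, so u = L / (p × s + 1 − p). TAU is taken as fully followed, or lost without regard to IPV. The odds ratio under no effect is (1 − w)/(1 − u).

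- L = 20%, s = 1.5: u = 0.20/1.10 = 0.182, w = 0.273, OR = 0.727/0.818 = 0.89.
- L = 20%, s = 2: u = 0.20/1.20 = 0.167, w = 0.333, OR = 0.667/0.833 = 0.80.
- L = 10%: OR 0.95 (s = 1.5) or 0.91 (s = 2). L = 30%: 0.81 or 0.67.
- s = 1: OR 1.00 at every L.
- s = 0.67, where violent families complete more often: OR 1.04 to 1.16 for L from 10% to 30%.

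Varying p from 10% to 40% at L = 20% gives 0.88 to 0.90 for s = 1.5 and 0.78 to 0.83 for s = 2.

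In the two L = 20% cases the completer IPV rates are 18.2% and 16.7% against 20% in TAU. With 60 TAU families and 48 completers (60 × 0.8), a nominal 5% two-sided test rejects in about 5.6% and 7.1% of trials (normal approximation).

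**Step 2. Non-randomised families in the FIOC condition.** Suppose 75 randomised FIOC families have 20% IPV and the 20 added families have a different rate. The TAU odds are 0.20/0.80 = 0.25.

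- Added families at 10%: (75 × 0.20 + 20 × 0.10)/95 = 17/95 = 0.179; odds 0.218; OR = 0.218/0.25 = 0.87.
- Added families at 30%: (15 + 6)/95 = 21/95 = 0.221; odds 0.284; OR = 0.284/0.25 = 1.14.
- Added families at 20%: OR 1.00.

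**Step 3. Precision lost by restricting to randomised families.** If 60 of 95 FIOC families are followed, the randomised share is 75 × 60/95, about 47. At 20% IPV:

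- 60 v 60: √(1/12 + 1/48 + 1/12 + 1/48) = 0.456.
- 47 v 60: √(1/9.4 + 1/37.6 + 1/12 + 1/48) = 0.487.

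The ratio is 1.07. The projection of 60 per arm may predate the extension to 170, so the 47 is only an example.

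**The case against.** The strongest reply is that the SAP does not plan a completer analysis. It is the later document and speaks of conditions and intervention group, and Protocol section 4 uses the same language for what the urn allocates. That section also reminds all families of the 3- and 12-month assessments whatever their assignment. The natural reading is comparison by assigned condition. This stands: Step 1 measures the contrast in Hypothesis 8, not the SAP analysis. What the reply leaves is that the SAP does not state its analysis set, and that assigned condition in FIOC includes families who were not randomised.

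Safeguards also exist. The urn balances frequency of IPV, serious IPV is an exclusion ("Any referred families with more significant and serious IPV are ineligible for participation in the study"), and the second and third SAP analyses use baseline CTS2. These reduce the room for bias. But the urn does not act on later completion or on families outside it, and the chi-square is unadjusted.

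A further reply is that a missing analysis set and the non-randomised families affect every FIOC v TAU comparison. That is true. The one-arm completion condition, however, is particular to Hypothesis 8 among the between-arm hypotheses.

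A reader might go further and infer that violence-related dropout will bias the trial towards FIOC. Section 13 does allow withdrawal ("If a family must be withdrawn from the project based on assessments of concerns around safety"), and the added FIOC families suggest fewer FIOC families were being followed. But the documents do not show that loss is related to IPV. With 60 of 75 TAU families followed, 20% IPV and violent families lost 1.5 to 2 times as often, the exact chi-square rejection rate is 5.2% to 6.5% at 71% to 75% FIOC retention, against 5.1% to 5.3% with no bias. It reaches 6.0% to 9.6% only at 63% retention, a figure (60/95) that may combine two versions of the plan. With equal loss the odds ratio is 1.00.

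**Conclusion.** The point holds in a limited form. Hypothesis 8 is worded as a completer contrast in one arm. The SAP probably intends comparison by assigned condition but does not say so, and that condition can include up to 20 families placed without randomisation. Neither text, followed as written, is purely the randomised comparison.

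The size cannot be taken from the documents, which give no IPV rate, completion rate or link between the two. On the assumptions shown, the completer contrast gives an odds ratio of 0.89 to 0.80 at 20% non-completion, and the added families move it to 0.87 or 1.14. Both effects vanish if completion is unrelated to IPV and the added families resemble the rest, and both can go the other way. A reader might infer that the planned analysis is biased in favour of FIOC; the documents do not support that. The aim is exploratory, so this is a low-priority correction.

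**What to change.** Restate Hypothesis 8 and SAP Exploratory Aim 2 so that the main IPV comparison is the families randomised by urn (the first 150), by assigned arm, whether or not they completed FIOC. Show the non-randomised FIOC families separately, or include them only in a labelled all-families sensitivity analysis. Label any completer contrast as secondary and non-randomised. Keep the baseline-CTS2 models as planned.

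The cost is a few sentences and some precision. Up to 20 of about 95 FIOC families (21%) leave the main comparison, and in the example of Step 3 the standard error of the log odds ratio rises from 0.456 to 0.487. The change removes the completion and non-randomised elements from the main comparison. It does not remove any bias from violence-related loss to follow-up, should that occur. No withdrawal or safety rule is affected.
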